CM for alcohol will be adapted from prior research.³² The COMpAAAS RIB will design a web-based program to track CM visits and rewards. CM visits will occur every 3 weeks to correspond with the time frame of abstinence detected by PEth. This will help to minimize patient demands with respect to clinic visits. CM visits will be provided by clinic Social Workers and will occur once every 3 weeks over 3 months (4 sessions). Rewards will be obtained through “draws” of paper slips from a bowl (fishbowl). The slips in the bowl will be set up in accordance with preset (See below) probabilities of rewards. For the VA sites, the rewards will be provided as VA coupons in specific dollar amounts that can be used to purchase items at a VA Canteen store (similar to Walmart and Target stores). This strategy has been used successfully in CM programs in the VA.³³ At the beginning of treatment, the Social Worker will visit the local Canteen store with patients and have them identify items that they wish to purchase with their rewards. For the non-VA site, the research coordinator will add any funds rewarded to a ClinCard.

The bowl from which patients will draw will contain 100 slips of paper. Twenty slips will state “Good job” but not be associated with any tangible earnings. Sixty-four of the slips will state “Medium Prize” and be associated with a \$5 reward, 15 will state “Large Prize” and be associated with a \$25 reward, and one will state “Jumbo Prize” and be associated with a \$100 reward. For VA sites, dollar amounts earned will relate to coupons for use at the local VA Canteen store. For the non-VA site, dollar amounts will be added to a reloadable ClinCard.

At each CM visit, patients will undergo a blood alcohol content analysis (BAC) with a breathalyzer or saliva test and provide a finger stick blood sample for PEth testing. The research coordinator will take a digital photo of the bloodspot collection card. The photo, which will not contain any identifiers (the study ID only) will be sent to the Yale Coordinating Center for approval. Once the sample is approved, the research coordinator will then ship the sample to the lab for testing. The BAC and PEth results will determine whether patients receive rewards for abstinence. Since PEth testing cannot take place onsite, PEth results will be available within 72 hours.

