Patients in the CM plus stepped care arm who have PEth > 8 ng/ml at 3 months will progress to Step 2 and receive onsite treatment from an Addiction Psychiatrist (APM) and MET from the Social Worker in the HIV clinic. APM will provide care that is typically provided by physicians in specialty referral programs. We have used this model successfully in earlier trials.^{35,67} After an initial 45-minute evaluation session, the physicians will administer APM weekly for 2 weeks, every 2 weeks for 4 weeks and then monthly. The physician will 1) assess the impact of alcohol use on medical, psychiatric, social, employment, and legal functioning, 2) educate the patient about alcohol, 3) prescribe alcohol pharmacotherapy if indicated, 4) encourage abstinence and adherence to medication (as appropriate); 5) encourage lifestyle changes, avoidance of triggers and attendance at mutual-help groups; 6) identify and address medical complications of alcohol use; and 7) refer patients to indicated treatment services (e.g., vocational, housing or social service). Medications are useful adjuncts to counseling in initiating abstinence and preventing relapse in patients with AUD. Disulfiram, oral naltrexone, injectable naltrexone, and acamprosate are available at the seven sites. Naltrexone has the best evidence of efficacy and⁶⁸ we have demonstrated the safety of naltrexone in HIV-infected patients.⁶⁹ In addition, we have completed a trial of injectable naltrexone in HIV-infected heavy drinkers. We allow the

physicians flexibility with respect to choice of pharmacotherapy for a more “real world” implementation. Decisions to not offer alcohol pharmacotherapy for those with AUD will be discussed on a case by case basis with [name] or [name] in light of contraindications.⁷⁰ In addition, monthly supervision phone calls will encourage use of pharmacotherapies where appropriate. The prescribing physicians will have the final decision as to the medication, dose, and duration. Medications will be tracked through assessments and the EHR.

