MET will be provided in 4 sessions to coincide with the initial APM visits. At the first MET session with the social worker, participants will be given a personal feedback report which will provide the participants with information on their current drinking habits as well as how their drinking may affect their current health status. We will use the MET manual (based on [name] [a consultant on the current protocol] ELM Brief Intervention Study Treatment Manual) that we are using in the current **STEP** Trials that includes adaptations for HIV-infected patients. MET is grounded in research on processes of natural recovery during which patients move through stages of change – precontemplation, contemplation, determination, action, and maintenance.⁷¹ The Social Worker’s role is to assist the patient in moving through the stages of change. MET uses motivational interviewing and reflective listening to help patients identify internal sources of motivation to support reductions in alcohol. We have selected MET as a counseling platform because 1) it is consistent with the use of alcohol medications, 2) the efficacy is equivalent to other manualized therapies⁷² 3) it has applicability to a range of behavioral challenges encountered in medical settings (e.g. diet, smoking), 4) training in motivational interviewing is widely available, and 5) because it has the flexibility to address patients across a spectrum of readiness to change their alcohol use.⁷³⁻⁷⁵

Due to the declared public health emergency in March 2020, the MET and APM sessions will be done by videoconference or telephone. This will limit participants’ and employees’ exposure to COVID-19.

Training and supervision of study interventionists

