Assessments at 9 and 12 months will include: PEth testing, pharmacy fill/refill data for ART, TLFB, VACS index, HRBS, ASI, PHQ-9, TSR, exhaled CO test or urine cotinine as indicated, HCV as indicated, past 30 day prescription of psychoactive medications that interact with alcohol. We will additionally assess measures of health care utilization (e.g. ED visits, hospitalizations, medications prescribed) based on the VA EMR or Epic. At the end of study participation all VA subjects will be offered enrollment in VACS for continued follow up.

Due to the declared public health emergency in March 2020, the assessments are done by videoconference or telephone. This will limit participants' and employees' exposure to possible COVID-19 exposure. Participants will receive \$50 upon completing the telephone assessment. We will ask participants to complete the visit when conditions permit them to come to the clinic to conduct laboratory and PEth testing.

Participant compensation for completing assessments

Participants will be compensated \$50 completing each assessment at baseline assessment, during treatment (3 months), end of treatment (6 months) and the follow-up assessment at 9 and 12-months. The total possible compensation for completing study assessments is \$250. Patients randomized to CM plus stepped care patients may earn more depending upon their response to treatment. In addition, patients randomized to CM plus stepped care will receive \$15.00 per intervention visit to cover travel costs.

1. Genetic Testing N/A

A. Describe

- i. the types of future research to be conducted using the materials, specifying if immortalization of cell lines, whole exome or genome sequencing, genome wide association studies, or animal studies are planned
- ii. the plan for the collection of material or the conditions under which material will be received
- iii. the types of information about the donor/individual contributors that will be entered into a database
- iv. the methods to uphold confidentiality

B. What are the conditions or procedures for sharing of materials and/or distributing for future research projects?

C. Is widespread sharing of materials planned?

D. When and under what conditions will materials be stripped of all identifiers?

E. Can donor-subjects withdraw their materials at any time, and/or withdraw the identifiers that connect them to their materials?

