Procedures for training and supervision of RAs and audio file raters have been developed as part of our previous and current studies. Initial training utilizes intensive seminars on all of the research instruments, after which the RAs observes the trainer administer the assessments and co-rates the assessments. Subsequently, the RA will conduct the assessments and make the ratings with the trainer present for a minimum of five full assessments and until complete agreement is obtained. During the study, the Project Coordinator, [name] will review all assessments and provides feedback on the completeness, accuracy or errors in the rating forms. Continued supervision and training on all instruments is provided on a regular basis to insure continued reliability of the assessments. RAs and tape raters are not involved in the provision of treatment to patients and are not informed about the treatment assignments.

All clinical aspects of the study, such as treatment delivery and monitoring of subjects' progress or the lack of thereof are also fully documented and supervised. The research team meets weekly to review the overall progress of the study, as well as to review digitally recorded sessions and/or discuss progress of each subject in the study. All members of the research team, both research assistants and clinicians, are familiar with procedures for identifying and reporting possible adverse reactions.

All adverse events are reported using the Yale Institutional Review Board (IRB) standard template for reporting adverse events. The Principal Investigator (PI) reviews all adverse events, classifies the attribution of adverse events (e.g., definitely, probably, possibly related; unlikely or unrelated) and grades the severity of the event, utilizing the FDA's definition of serious adverse events, on a 6-point scale (0=no adverse event or within normal limit; 1=mild; 2=moderate; 3=severe; 4=life-threatening; 5=fatal). Serious adverse events will be reported within 48 hours to the NIAAA project officer. Serious and unanticipated and related adverse events or unanticipated problems involving risks to subjects or others will be reported in writing within 48 hours to the Yale IRB. A summary of adverse events will be reported annually to the

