[name]. will serve as Chair of the Data Safety and Monitoring Board (DSMB) which will be composed of another expert in clinical trials in alcohol treatment and an expert in statistical analysis of clinical trials. Twice annually the DSMB will review the progress of the study and frequency of serious adverse events.

- d. For multi-site studies for which the Yale PI serves as the lead investigator:
 - i. How will adverse events and unanticipated problems involving risks to subjects or others be reported, reviewed and managed?

All adverse events are reported using the Yale Institutional Review Board (IRB) standard template for reporting adverse events. The Yale Principal Investigator (PI) reviews all adverse events, classifies the attribution of adverse events (e.g., definitely, probably, possibly related; unlikely or unrelated) and grades the severity of the event, utilizing the FDA's definition of serious adverse events, on a 6-point scale (0=no adverse event or within normal limit; 1=mild; 2=moderate; 3=severe; 4=life-threatening; 5=fatal). Serious unanticipated or anticipated adverse

events will be reported immediately to the IRB and to NIAAA. Adverse events will be reported in summary form at least annually to the IRB. The summary will include the number of subjects enrolled and a summary of graded adverse events to date, using the chart format included in the Yale University DSMP template. The PI will evaluate all adverse events and determine whether the event affects the Risk/Benefit ratio of the study and whether modifications to the protocol (e.g., Risks to Subjects) or consent form (e.g., Risks and Inconveniences) are required.

ii. What provisions are in place for management of interim results?

No interim analyses will be performed

iii. What will the multi-site process be for protocol modifications?

There will be one protocol document and each participating institution will utilize that document. The Yale PI is responsible for the coordination of the approval of the protocol as well as its subsequent amendments and will be responsible to ensure that the sites are using the correct version of the protocol. The Yale PI will collect and maintain copies of all IRB approvals from each site and will collect and review conflicts of interest declarations made by the Site PIs.

9. Statistical Considerations: Describe the statistical analyses that support the study design.

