Based on the existing literature on interactions between NTX and ART, these interactions should be clinically insignificant. Many of the medications used for the treatment of HIV are metabolized via the cytochrome P-450 system (CYP450) leading to issues surrounding drug interactions with a number of medication classes. The metabolism of NTX, however, is not entirely metabolized via CYP450 and therefore significant interactions with ART medications would not be expected ^{119,120}. A large multi-center safety study of the use of NTX for alcoholism in 865 individuals, including patients with comorbid psychiatric illness, concomitant medications, polysubstance abuse, and HIV demonstrated that serious side effects in these populations were uncommon ¹²¹. While this study was not randomized in design and was intended to look at medication interactions, the findings are reassuring for patients with HIV disease. Extended release NTX is approved for use in patients who meet criteria for Childs-Pugh A and B liver disease. While these data are reassuring, monitoring of liver function, to assess for hepatotoxicity, will be important, especially in HIV/HCV co-infected patients. The proposed study will systematically examine the question of medication interactions by closely following for adverse effects.

Acamprosate: The most common and persistent side effect of acamprosate is diarrhea. Less common side effects include suicidal ideation, intestinal cramps, headache, flatulence, increased or decreased libido, insomnia, anxiety, muscle weakness, nausea, pruritus, and dizziness. The dose of acamprosate needs to be adjusted based on renal function. Diarrhea can be managed with medications that slow gastrointestinal motility. There are no known medication interactions between acamprosate and ARVs.

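### The plan promises to study drug interactions by following adverse effects, but it schedules no adverse-event question and gives the CM arm far more contacts at which events can surface

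*Combined protocol and SAP*

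**What the plan says.** The commitment appears once, in the discussion of naltrexone and ART in Section VI, A.2: "The proposed study will systematically examine the question of medication interactions by closely following for adverse effects". The parallel naltrexone text under Risks (Section V.6) lacks the sentence, and drug interactions are not among Aims 1 to 3 (Section V.1).

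**Data collection.** Table 3 (Section V.3) lists the assessments at baseline, week 12, week 24, month 9 and month 12. It has no AE row. In both arms it does include AST, ALT, creatinine, hemoglobin, HIV viral load, ART adherence, alcohol medications, ED visits and hospitalizations.

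**Safety procedures.** Section V.8 promises procedures for prompt discovery of events but names no question, checklist, recall window or visit. It then deals with events already known: "All adverse events are reported using the Yale Institutional Review Board (IRB) standard template for reporting adverse events". The PI attributes and grades them, and graded summaries go to the IRB at least annually. For the DSMB: "Twice annually the DSMB will review the progress of the study and frequency of serious adverse events".

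**Analysis.** Section V.9 has no safety population, AE table or drug-by-ART analysis, and its interim monitoring list has no safety item.

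**Contacts.** Both arms have the common assessments. Only the CM arm has four CM sessions, three weeks apart. On Step 2 the plan says "Patients in the CM plus stepped care arm who have PEth > 8 ng/ml at 3 months will progress to Step 2". After an initial evaluation there, "the physicians will administer APM weekly for 2 weeks, every 2 weeks for 4 weeks and then monthly". In addition, "MET will be provided in 4 sessions to coincide with the initial APM visits".

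**The concern.** With no scheduled enquiry, a non-serious symptom enters the record mainly when a participant mentions it to study staff. The CM arm meets staff far more often, so equal true rates can look unequal. The symptoms that Section VI lists for naltrexone (nausea, headache, insomnia) are of this volunteered kind. Anyone who later reports AEs by arm could mistake a difference in ascertainment for a difference in harm.

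The second problem is separate. A reader of Section VI would expect the trial to yield evidence on interactions between alcohol drugs and ART, and the design and analysis plan do not provide for that.

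**Working it through.** The plan gives no AE rate, contact count or safety power, so there is no figure of its own to reproduce.

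**1. Contacts after baseline, to week 24**

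CM sessions are taken at weeks 3, 6, 9 and 12, the last coinciding with the week-12 assessment. Addiction Physician Management (APM) is an evaluation, 2 weekly visits, 2 fortnightly visits and 1 monthly visit, taken at weeks 13, 14, 15, 17, 19 and 23. MET sessions are merged with APM visits.

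- TAU: weeks 12 and 24 = 2.
- CM, not stepped up: weeks 3, 6, 9, 12 and 24 = 5 (5/2 = 2.5 times TAU).
- CM, stepped up: 5 + 6 = 11 (11/2 = 5.5 times TAU).

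If the fourth CM session is separate from the week-12 visit, the CM counts become 6 and 12. A seventh APM visit and four separate MET sessions would bring the highest count to 17.

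**2. Effect on ascertainment, equal true rates**

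Assumptions: a non-serious event is recorded only if a contact follows within r weeks, and events are spread evenly over the period. The share of the CM arm stepped up is taken from the planning abstinence rates of 26% and 11%: 1 − 0.26 = 74% and 1 − 0.11 = 89%. Those are 6-month rates, used here for month 3.

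Capture = weeks lying within r weeks before a contact, divided by 24.

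Worked example, r = 2:
- TAU: 4/24 = 16.7%.
- CM, not stepped up: 10/24 = 41.7%.
- CM, stepped up: 18/24 = 75.0%.
- CM arm: 0.74 × 75.0 + 0.26 × 41.7 = 66.3%, or 0.89 × 75.0 + 0.11 × 41.7 = 71.3%.
- Ratio: 66.3/16.7 = 4.0 to 71.3/16.7 = 4.3.

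| r (weeks) | TAU | CM not stepped up | CM stepped up | CM arm | Ratio to week 24 | Ratio over 52 weeks |
|---|---|---|---|---|---|---|
| 2 | 4/24 | 10/24 | 18/24 | 66–71% | 4.0–4.3 | 2.5–2.6 |
| 4 | 8/24 | 16/24 | 24/24 | 91–96% | 2.7–2.9 | 1.9 |
| 6 | 12/24 | 18/24 | 24/24 | 94–97% | 1.9 | 1.4–1.5 |
| 8 | 16/24 | 20/24 | 24/24 | 96–98% | 1.4–1.5 | 1.2 |
| 12 | 24/24 | 24/24 | 24/24 | 100% | 1.0 | 1.0 |

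The 52-week column adds the common visits at weeks 39 and 52 to both arms.

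A second model gives a similar message. If each contact picks up an event with probability d, capture = 1 − (1 − d)^contacts. For 4 against 14 contacts over 12 months (4 common visits; plus 4 separate CM sessions and 6 APM visits), the ratio is 2.24 at d = 0.1, 1.62 at 0.2, 1.31 at 0.3 and 1.07 at 0.5.

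**3. Information on interactions**

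With 348 randomized and 1:1 allocation assumed, each arm has 174. Step 2 would take 0.74 × 174 = 129 to 0.89 × 174 = 155 people. If 10% to 50% of them receive a given drug (assumed), 13 to 77 are exposed in Step 2. With no events seen, the one-sided 95% upper limit is 1 − 0.05^(1/n): 21% at n = 13 and 4% at n = 77. This omits exposure in Step 1 and in TAU, and the exposed group would shrink further if split by ART regimen.

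**The case against.** Four points on the other side deserve weight.

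- **Safety is not ignored.** A reader might infer that the trial collects no AE data and has no safety review. The documents do not support that. Section V.8 provides attribution, grading, summaries and DSMB review of serious events, and Table 3 collects laboratory values, medications, ED visits and hospitalizations identically in both arms. This stands. The gap is confined to non-serious, volunteered events.
- **No by-arm AE comparison is planned, so nothing pre-specified is biased.** This also stands. Section V.8 has the PI weigh each event for risk and benefit, not compare arm rates. The bias would arise only if events were tabulated by arm.
- **The size rests on a recall window the plan does not give.** Correct. A reader might infer that CM rates will be inflated several-fold, but at 12 weeks the ratio is 1.0. The Treatment Services Review already asks about services since the last assessment, which shows that a long window is workable.
- **Alcohol drugs are not confined to one arm.** A reader might infer that they are. But Step 1 can reward receipt of alcohol pharmacotherapy (Section V.3). TAU providers are told of an alcohol use disorder and may refer, and the drugs come through routine care (Sections V.3, VI A.3 and X.1).

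What survives is that no elicitation step is specified, contact is unequal, and the Section VI sentence claims more than the plan delivers. Filling the gap by logging events at every contact would keep the imbalance.

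**Conclusion.** The point holds in a limited form. Non-serious, volunteered events are likely to be found more often in the CM arm, and any by-arm report of them would carry that bias. Its size ranges from a ratio of about 4 to none, depending on the recall window, under the assumptions of equal true rates, evenly spread events and 74–89% stepped up. Serious events are largely protected by the common data sources.

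The interaction question fails for a different reason. It might be inferred that unequal contact is what leaves it unanswered, but an interaction between an alcohol drug and ART is not the randomized contrast, so contact counts by arm do not decide it. It goes unanswered because drugs are given non-randomly (mainly in CM Step 2, but possibly also in Step 1 and in TAU) and no exposure groups or analysis are defined.

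This is a cheap improvement. It does not touch the efficacy analysis.

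**What to change.** 1. Add one identical open AE question to Table 3 at week 12, week 24, month 9 and month 12 in both arms, covering the time since the last common assessment.
2. State in Section V.9 that any between-arm comparison of non-serious AEs uses events elicited at those visits, plus ED visits and hospitalizations from the health record.
3. Show events found at CM, APM or MET visits in a separate table by arm. Every event, wherever found, still goes to the PI, the DSMB and the IRB.
4. Reword the Section VI sentence to say that the study will monitor and describe adverse effects in participants who receive alcohol pharmacotherapy.

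The cost is one question at four existing visits, a descriptive table and a wording change. The downside is that the between-arm comparison uses fewer events than the full log. Participants also know their treatment, so a common question evens out the opportunity to report but not every difference in willingness to do so.
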